- g ECG will be performed at screening
- h Clinical laboratory tests will include hematology and serum chemistry panel including white blood cell count, differential, hemoglobin, platelet count, sodium, potassium, chloride, bicarbonate, BUN, creatinine, glucose, calcium, and magnesium, SGOT, SGPT, and total serum bilirubin, albumin, and total protein. Additional tests will be performed when clinically appropriate. In case of Grade 3 or higher abnormal liver function results, additional testing will be done weekly until recovery to baseline value (see section 7.2). For all other timepoints, labs can be performed up to 3 days prior to each timepoint indicated in the study calendar (other than required C1D1 timepoint). Results from labs obtained on C1D1 do have to meet eligibility criteria.
- i FPG (fasting plasma glucose) will be collected at screening, on Days 1 and 15 of C1, on CXD1 of subsequent cycles, and at the End-of-treatment visit. FPG will also be monitored if patients experience Grade ≥1 hyperglycemia during the course of the study per the hyperglycemia management guidelines provided in the protocol. FPG can be obtained up to 3 days prior to each timepoint indicated in the study calendar (other than required C1D1 timepoint). Fasting plasma glucose is the same as serum glucose on days that the patient is fasting. On days the patient is getting non-fasting labs, it should be serum glucose only. (See Table 3 under section 7.2.1.5)
- j Serum pregnancy test: women of child bearing potential must have a negative serum pregnancy test result within 28 days prior to the initial dose of IMP.

- k PKs for patients in the phase Ib portion: plasma sample should be obtained on Cycle 1, day 8 at: 0-4 hours prior to dose of taselisib and 1, 3, and 6 hours post administration taselisib. On Cycle 2, day 15 at: 0-4 hours prior to dose of taselisib and enzalutamide and 1, 3, and 6 hours post administration taselisib and enzalutamide. On Cycle 4, day 1, plasma sample should be obtained 0-4 hours before taselisib and enzalutamide administration, and 3 hours post-administration of both drugs. PKs in phase II will occur for 10 patients at the Vanderbilt site only and should be obtained on patients receiving both enzalutamide and taselisib: C2D1, C2D15, and C4D1 at 0-4 hours prior to taselisib and enzalutamide and 2 to 4 hours post treatment.

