- l Tumor assessment should be performed approximately every 2 cycles (up to -5 days) while on study treatment and at End-of-treatment visit if not obtained within the past 6 weeks. Scans should consist of CT scan of the chest, abdomen, and pelvis and a bone scan at baseline. Subsequent scans should consist of CT chest, abdomen and pelvis, and bone scan if bone metastases were present on the baseline studies. At the end of treatment, all scans (baseline and through disease progression) should be sent on a CD to the Vanderbilt Cancer Imaging Support Laboratory for central review and assessment. See Section 10.5 for details and address.
- m Archived tumor biopsy specimen: 20 unstained slides of archived biopsy block (unstained slides) or fresh tumor biopsy will be requested at the time of enrollment prior to initiation of treatment.
- n Tumor biopsies will only be performed in the phase II portion. A tumor biopsy from a metastatic site will be obtained from patients prior to day 1, at cycle 2 day 14-21, and upon progression of disease. The third biopsy (at the end of treatment) will not be required for patients who are removed from study for reasons other than disease progression. A patient who undergoes a research biopsy procedure for the purpose of this protocol, and in whom inadequate tissue is obtained, is not obligated to undergo a repeat biopsy.
- o See section 9.1. Required only for patients at Vanderbilt and only in the phase II portion. This should be performed prior to tumor biopsy, if possible. If MRI sub-study is not feasible due to scheduling, MRI weight limits, etc., patients may still continue with the remainder of the study.
- p Subjects on the enzalutamide + taselisib arm should begin enzalutamide on day 1 of cycle 1, and taselisib on day 1 of cycle 2.
- q Pill Diary can be found in the packet of supplemental forms.
- r See Section 6.4.2.
- s Phase II only. Biopsy questionnaire should be filled out by the patient on C3D1. Form can be found in the packet of supplemental forms.
- t The cycle 2 day 8 visit is only needed for patients on the combination of taselisib + enzalutamide. Patients on enzalutamide only do not need a visit on this day.

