### 6.2.3 Definition of Maximum Tolerated Dose (MTD)

The MTD was defined as the highest dose of taselisib tested in which a DLT is experienced by 0-1 out of 6 patients among the dose levels. The dose of enzalutamide remained constant. The first cohort of patients (3 patients) in each arm started at dose level 1, and each patient was observed for 4 weeks on the specified dose and instructions were followed as below:

- If no patient in the first cohort of 3 experiences a DLT, dose escalation will proceed and patients will be accrued at the next dose level. If 1 of these patients experiences a DLT, the cohort will be expanded to 6 patients. If <33% of these patients experiences a DLT (e.g., 1 of 6 patients), dose escalation may proceed.
- If a DLT is observed in  $\geq 33\%$  of the patients in a given cohort (e.g.  $\geq 2$  of 6 patients), the MTD will have been exceeded and the lower dose level will be evaluated.

An exception to the above rule would be in the case in which the two DLTs observed out of 6 patients are both hematologic in nature and potentially reflect poor bone marrow reserve in this heterogeneous patient population and not the true MTD for the combination. In this instance, up to 3 additional patients may be enrolled to expand the total cohort size to 9 patients to assess for further DLT. In this situation, if a third DLT is observed, the MTD will have been exceeded and the lower dose level will be evaluated.

- If the 2 mg dose does not exceed the MTD, then dose escalation will proceed to the 4 mg dose. If the 4 mg dose does not exceed the MTD, then dose escalation will proceed to the 6 mg dose, and if the 6 mg dose does not exceed the MTD, then dose escalation will proceed to the 8 mg dose. If <33% of patients experience a DLT in the 8 mg cohort, then this dose level will be the maximum administered dose (MAD).

No new cohort of patients will be treated until the previous cohort has been fully evaluated for toxicity. Patients requiring dose reduction for reasons other than a DLT in cycle 1 of the phase Ib portion will not be included in the DLT evaluation. If the frequency of Grade 3 or 4 toxicities or other unacceptable lower grade chronic toxicities in the phase 1b portion suggests that the MTD has been exceeded at that dose level, any remaining accrual at that dose level will be halted and a lower dose of taselisib may be examined.

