### 6.3.1 Taselisib

Taselisib tablets are administered once daily until disease progression or intolerable toxicity. Taselisib administration will begin on C2D1 for patients enrolled on the combination arm (with enzalutamide alone beginning on C1D1). Each dose should be taken with a minimum of 3–4 ounces (90–120 mL) of water with or without food in the morning (before noon). If a dose is missed (not taken by noon), the patient will resume dosing with the next scheduled dose. Missed or vomited doses will not be made up. The occurrence and frequency of any vomiting during a treatment cycle must be noted as an adverse event. Patients should swallow the capsules as a whole and not chew or crush them.

A sufficient number of taselisib tablets should be provided to the patient to last until the next cycle. Patients will be instructed to bring their bottles of study drug and their medication diary with them to each study visit.

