#### 7.2.1.3 *Dermatological Toxicity*

Treatment-related rash, including cases of Grade 3 rash, has occurred in patients who received taselisib. This rash is commonly manifested as maculo-papular with or without pruritus. Incidence rate and severity of rash appear to be dose dependent. The rash has resolved upon holding of taselisib and/or supportive therapy (e.g., topical or systemic steroids). Rash and other dermatological events should be closely monitored, and patients with severe rash should be monitored for associated signs and symptoms such as fever and hypotension that may be suggestive of a systemic hypersensitivity reaction. For severe rash, dosing of taselisib should be interrupted, and patients should be treated with supportive therapy per standard of care. Use of topical antihistamine, as well as topical or systemic corticosteroids, may be considered. Dose delay and modification guidelines for patients who experience rash are outlined in Table 3. Of note, no grade 3 or 4 rashes were noted in the phase Ib portion of this study with dose escalation to 8 mg taselisib. However, in the phase II portion with taselisib at 4 mg, 7 of 8 patients on the combination arm experienced a grade 3 or 4 rash with fever within the first 14 days of treatment. No patients who crossed over from enzalutamide to taselisib + enzalutamide experienced the rash, thus the study is amended so that all patients have a 28 day lead-in with enzalutamide prior to starting taselisib (similar to the cross-over arm). The rash resolved in all patients with IV steroids, antihistamines and supportive care.

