**\*\*Specimens should be mailed to arrive at VUMC from Monday 8AM through Friday 1PM\*\***

### 9.5 Pharmacokinetic Sampling

Pharmacokinetic sampling will occur in the phase Ib portion and in 10 patients in the phase II portion (phase II at Vanderbilt only). PKs for patients in the phase Ib portion: will be obtained on cycle 1, day 8 at: 0-4 hours prior to dose of taselisib and 1, 3, and 6 hours post administration taselisib; on cycle 2, day 15 at: 0-4 hours prior to dose of taselisib and enzalutamide and 1, 3, and 6 hours post administration taselisib and enzalutamide; on cycle 4, day 1, plasma sample should be obtained 0-4 hours before taselisib and enzalutamide administration, and 3 hours post-administration of both drugs.

The first ten subjects on the enzalutamide + taselisib arm at Vanderbilt should initiate taselisib on day 1 and enzalutamide on day 9 to facilitate PKs, which will be done on the first 10 Vanderbilt patients on the combination arm only. PKs in phase II (Vanderbilt only) should be obtained on patients receiving both enzalutamide and taselisib on C1D8, C2D15, and C4D1 at 0-4 hours prior to taselisib and enzalutamide and 2 to 4 hours post treatment. Please see the lab manual for details of collection and for information about shipping the samples.

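### Section 9.5 still starts taselisib before enzalutamide in the first ten Vanderbilt combination patients, against the 28-day enzalutamide lead-in adopted after severe rash in 7 of 8

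*Combined protocol and SAP*

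**What the plan says.** Section 7.2.1.3 records this for phase II, where the taselisib dose is 4 mg daily: "7 of 8 patients on the combination arm experienced a grade 3 or 4 rash with fever within the first 14 days of treatment". It reports no rash of that grade in phase Ib, where doses went up to 8 mg. The remedy follows in one sentence: "No patients who crossed over from enzalutamide to taselisib + enzalutamide experienced the rash, thus the study is amended", so that every patient takes enzalutamide for 28 days before taselisib. It adds: "The rash resolved in all patients with IV steroids, antihistamines and supportive care".

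The new order appears in these places:
- Study calendar, footnote p: "Subjects on the enzalutamide + taselisib arm should begin enzalutamide on day 1 of cycle 1, and taselisib on day 1 of cycle 2".
- Section 6.3.1: "Taselisib administration will begin on C2D1 for patients enrolled on the combination arm".
- Study calendar, footnote k, which sets phase II PK sampling for ten Vanderbilt patients "receiving both enzalutamide and taselisib: C2D1, C2D15, and C4D1". Section 6.3.2 sends the first ten Vanderbilt combination patients to the calendar for their PK draws.

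The old order remains in two places:
- Section 9.5, as a current instruction: "The first ten subjects on the enzalutamide + taselisib arm at Vanderbilt should initiate taselisib on day 1 and enzalutamide on day 9". The same paragraph puts the phase II PK samples on C1D8, C2D15 and C4D1.
- Section 6.2.1, in the past tense, for Vanderbilt combination patients in phase Ib or II.

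**The concern.** The lead-in is a safety measure, and 7.2.1.3 applies it to all patients with no exception for those giving PK samples. Section 9.5 gives the opposite order to a named group at the coordinating centre. PK staff are likely to work from that section, since it sets the sampling days. A site that followed 9.5 would expose patients to taselisib without prior enzalutamide, which the amendment was written to stop. A site that followed 6.3.1 would comply with the amendment but deviate from 9.5. The PK data would also be mixed, because the two sections disagree on the day of the first sample.

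**Working it through.** **Step 1: the two schedules, in days from cycle 1 day 1 (28-day cycles).**
- Lead-in (7.2.1.3, 6.3.1, footnote p): enzalutamide from day 1; taselisib from C2D1, which is day 28 + 1 = 29. Enzalutamide before first taselisib: 28 days.
- Section 9.5: taselisib from day 1; enzalutamide from day 9. Enzalutamide before first taselisib: 0 days.

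No patient can follow both.

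**Step 2: the PK day.** Section 9.5 wants phase II samples from patients taking both drugs, before and after both.
- On C1D8 under 9.5's own order, the patient takes taselisib only (day 8 is before day 9).
- On C1D8 under the lead-in, the patient takes enzalutamide only (day 8 is before day 29).
- On C2D1, the day in footnote k, both drugs are given.

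So C1D8 fails the section's own condition under either order, and footnote k fits the lead-in. This points to 9.5 as text that was not updated.

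**Step 3: the event behind the amendment.** 7/8 = 87.5%. Clopper-Pearson limits: lower, the 2.5% quantile of Beta(7, 2) = 47%; upper, 0.975^(1/8) = 99.7%.

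**Step 4: how many patients 9.5 could reach.** The cap is ten. If the 8 are all the combination patients so far (an assumption), between 0 and 8 of them were at Vanderbilt, so 10 - 8 = 2 to 10 - 0 = 10 places remain. If more had enrolled, fewer may remain.

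**Step 5: what the crossover group can show.** Its size is not given. Allocation of 3:1 against 8 combination patients suggests 8/3 = 2.7, about 3, and not all need have crossed over. For 0 events in n, the one-sided 95% upper limit is 1 - 0.05^(1/n). The Fisher two-sided p against 7/8 is C(8,7)/C(8+n,7) for these n.
- n = 2: limit 78%; p = 8/120 = 0.067
- n = 3: limit 63%; p = 8/330 = 0.024
- n = 4: limit 53%; p = 8/792 = 0.010

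At the likely size the data favour the lead-in but leave a wide range of true rates open.

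**The case against.** The conflict is narrow. It concerns one centre, and that centre coordinates the trial and distributes amendments. It covers at most ten patients. Section 7.2.1.3, 6.3.1 and footnotes k and p all give the amended order, and 6.2.1 speaks in the past tense. All of this stands, and it limits the size of the point. It does not make 9.5 correct: that paragraph is a live instruction.

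A reader might infer more in four ways that the documents do not support.

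- **That the taselisib-first order is known to cause the rash.** The plan does not say which order each of the 8 patients had. Section 6.2.1 says Vanderbilt combination patients in phase Ib took taselisib first, and no grade 3 or 4 rash was seen in that phase. The 88% therefore cannot be taken as the rate under 9.5.
- **That patients were in fact treated under 9.5 after the amendment.** Nothing in the plan says so.
- **That the lead-in fails the protocol's own 33% limit because the crossover group is too small.** Section 6.2.3 reads "If <33% of these patients experiences a DLT (e.g., 1 of 6 patients), dose escalation may proceed". That is an observed proportion, not an upper confidence limit, and escalation goes ahead after 0 of 3. Setting the 63% limit against 33% applies a test the protocol does not use.
- **That phase II has no protection if the lead-in fails.** Table 3 ends taselisib permanently for rash with fever. There is a C2D8 visit for combination patients. Section 11.3.2 requires SAEs to reach the coordinating centre within one business day. Sections 12.1 to 12.3 provide continuous monitoring by the Protocol Chair, monthly team meetings and site teleconferences, and DSMC review.

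The accrual halt in 6.2.3 is limited to phase Ib, and the boundary in 15.3 is for inefficacy, so phase II has no numeric rash trigger. Relying on judgement here is a choice with costs on both sides. As an illustration, pausing at 2 or more events in the first 6 patients would stop 89% of the time at a true rate of 50% (1 - 7/64), but also 34% of the time at 20% (1 - 0.8^6 - 6 × 0.2 × 0.8^5).

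**Conclusion.** The conflict in 9.5 is an error and should be corrected. It rests on the text alone: the two orders are incompatible, the lead-in is stated for all patients, and footnote k already has the matching PK day. The reach is up to ten Vanderbilt combination patients, or 2 to 10 if the 8 reported patients were all those enrolled so far. Each would start taselisib 28 days early, with no prior enzalutamide. The excess rash this would cause cannot be estimated from the plan.

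The missing crossover number and the absence of a phase II rash count are not errors. The first is a useful detail. With about 3 patients (assuming 3:1 allocation held and all crossed over), it supports the lead-in without settling the rate. The second is a trade-off for the sponsor and DSMC.

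**What to change.** Corrections:
- In 9.5, delete the taselisib-first instruction for phase II and replace C1D8 with C2D1, to match footnote k.
- In 6.2.1, limit the taselisib-first sentence to patients enrolled before the lead-in amendment.

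The cost is a text correction. Enzalutamide will already be on board at the first phase II PK sample, so that sample no longer shows taselisib alone; footnote k already accepts this.

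Optional, for the sponsor and DSMC:
- In 7.2.1.3, state how many patients had crossed over when the amendment was made.
- Consider a prespecified phase II count that prompts DSMC review. The event should be the one in 7.2.1.3 (grade 3 or 4 rash with fever), counted within 28 days of the first taselisib dose, because cycle 1 contains no taselisib under the lead-in. The boundaries should be coherent across looks, so that a count that pauses the trial early is not followed by a higher observed rate that does not.
- Any such rule should say how patients held on enzalutamide alone count in the CBR. Under 15.5 and 15.7, patients with four weeks of study drugs enter the efficacy analysis, so a pause could dilute the combination arm's primary result.

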#### 7.2.1.4 *Gastrointestinal Toxicity*

Nausea, vomiting, stomatitis, and diarrhea have been observed in patients receiving taselisib. Colitis was diagnosed by several methods, including endoscopy and abdominal imaging (computed tomography [CT] scans). Pathology from biopsies obtained from endoscopy has confirmed colitis. Patients usually present with Grade 2 or Grade 3 diarrhea that has been refractory to antidiarrheals. The time (from the first dose of study treatment) to onset (formal diagnosis of colitis) ranged from approximately 99–250 days. Patients had resolution or improvement of gastrointestinal toxicities upon holding study drug and/or initiating corticosteroid therapy. Perforated duodenal ulcer has been observed in 2 patients (1 patient at 6 mg in combination with letrozole; another patient at 6 mg in combination with fulvestrant. Appropriate caution should be taken with the administration of medications such as aspirin, NSAIDs, and corticosteroids, which can increase the risk of gastritis, peptic ulcers, or GI perforation.

Patients should be closely monitored for gastrointestinal symptoms (e.g., nausea, vomiting, diarrhea, abdominal pain, stomatitis, and changes in stool, including checking for blood in stool if clinically indicated). Patients should be advised to inform the investigator if any diarrhea occurs, even if it is mild. Prompt management of diarrhea with antidiarrheal medications should be implemented. Because of the approximately 40 hour half-life of taselisib, investigators should hold taselisib for Grade  $\geq 2$  diarrhea. Patients who resume treatment should be monitored closely for sign of renewed diarrhea.

Patients with inflammatory bowel disease, such as Crohn's disease or ulcerative colitis, are excluded from this study. Steroid-responsive diarrhea and colitis have been difficult to distinguish in patients treated with taselisib. All cases of colitis have been reversible with corticosteroid treatment. Prompt initiation of corticosteroids for persistent diarrhea despite anti-diarrheal treatment can decrease the severity of the diarrhea and prevent the need for hospitalization. Patients who develop severe steroid-responsive diarrhea usually have been on taselisib treatment for at

least 2 months, with an average onset 4 to 6 months of treatment. A stool culture is helpful in identifying concurrent infections, and patients have been successfully treated with concurrent steroids and appropriate antibiotics, if needed.

If a patient is being treated with corticosteroids, total parenteral nutrition is discouraged, as this increases the risk for severe hyperglycemia. Discontinuation of non-steroidal inflammatory medications or other medications that exacerbate colitis are also recommended during colitis episodes.

Management recommendations for GI toxicities are outlined in Table 3.

#### 7.2.1.5 Liver Toxicity

If clinical symptoms or signs suggestive of liver dysfunction occur (e.g., nausea, vomiting, abdominal pain, fatigue, anorexia, “flu-like” symptoms, dark urine, jaundice, or right upper quadrant tenderness), the serum transaminases should be measured immediately. Elevations above baseline should prompt an evaluation should occur to determine the cause of the elevation, including progressive disease and hepatotoxicity from concurrent medications.

If transaminases (ALT/AST) are elevated  $> 3X$  ULN and are thought to be secondary to disease progression, a CT scan should be obtained to confirm disease progression and the patient should be removed from study. If transaminases (ALT/AST) are elevated  $> 3X$  ULN and not thought to be secondary to disease progression, treatment should be withheld until levels fall to  $\leq 3X$  normal levels. If a patient has known liver metastases and baseline transaminases were 3-5X ULN, treatment should be held until levels fall to less than or equal to baseline levels. If total bilirubin is elevated  $> 1.5$  x normal level, treatment should be withheld until level falls to  $\leq 1.5$  x normal levels. If alkaline phosphatase is elevated  $> 2.5$  x normal value, treatment should be withheld until levels fall to  $\leq 2.5$  x normal level (unless bone metastases are present in the absence of liver metastases). A dose reduction should then be administered following resolution of any or all of these liver enzyme abnormalities.

If transaminases are subsequently elevated  $> 3X$  ULN or, if total bilirubin is elevated  $> 1.5X$  normal value, or if alkaline phosphatase is elevated  $> 2.5$  x normal value (unless bone metastases are present in the absence of liver metastases), treatment will again be withheld until AST/ALT decrease to  $\leq 3X$  normal, total bilirubin decreases to  $\leq 1.5$  x normal value and alkaline phosphatase decreases to  $\leq 2.5$  x normal value. A second dose reduction should then be administered. If a patient has known liver metastases and baseline transaminases were 3-5X ULN, treatment should be held until levels fall to less than or equal to baseline levels. For any hepatic toxicity CTCAE Grade 4, or CTCAE Grade 3 that does not resolve within 7 days to CTCAE Grade  $\leq 1$  (or CTCAE Grade  $\leq 2$  if liver infiltration with tumor present), an abdominal CT scan should be performed to assess if it is related to disease progression.

If, after 2 dose reductions, AST, ALT, total bilirubin and/or alkaline phosphatase remain elevated, patient should be taken off study, and laboratory abnormalities should be reported as an unacceptable toxicity.

